**Overview of Monitoring and Reporting:**

### **Monitoring of source data**

The clinical research coordinator will provide oversight to ensure all primary data are collected and entered into a database accurately.

### **Safety monitoring**

A 24-hour dedicated telephone line to the clinical research coordinator and/or physician will be provided for the subjects to call. Sponsor will adhere to commitments made to the Institutional Review Board.

### **Adverse event reporting guidelines:**

All adverse events must be reported in the subject's source documents, and recorded on an Adverse Event Case Report Form regardless of whether or not they are considered to be related to the test article. The recording should be within 24 hours of the time that the AE came to the attention of the Investigator. For non-serious AE it is sufficient to enter the AE information into the CRF. The Clinical Research Coordinator will review the database on a regular basis.

### **Reporting will include the actions taken, as follows:**

- None
- Subject discontinued from study
- Required concomitant medication
- Required procedure
- Other

Any action, including a decision that no action is required, must be documented by the Investigator on the source and CRF.

In the event of any SAE reported or observed during the trial, whether or not attributable to the trial product, the Investigator, or designee, shall report the event to the Sponsor within 24 hours being made aware of the event. An initial report should be made with the understanding that it may be lacking in detail. Serious adverse events must be reported within 24 hours of knowledge of the event to the Principle Investigator via telephone or email. All SAEs shall be entered into the CRF as soon as possible regardless of the method by which it was first reported. A Serious Adverse Event Form must be completed for all serious adverse events and submitted to the Sponsor within 24 hours of the Investigator's knowledge of the event, and to the Institutional Review Board/Independent Ethics Committee/FDA according to their reporting requirements. When new significant information is obtained as well as when the outcome of an event is known, the Investigator must provide this information as soon as it becomes available. Copies of the subject's de-identified medical records as well as results of any relevant laboratory tests performed should be submitted as soon as available. If the subject was hospitalized, a copy of the de-identified discharge summary should be forwarded as soon as it becomes available. In

certain cases, a letter from the Investigator that summarizes the events related to the case may be required.

The Investigator shall promptly notify the IRB and FDA of any SAEs, or any other information that may affect the safe use of the study product during the course of the study in accordance with applicable IRB policies and procedures.

BostonSight shall implement and maintain quality control and quality assurance procedures to ensure that the study is conducted and data are generated, documented, and reported in compliance with the protocol, GCP, and applicable regulatory requirements. Specifically, this study shall be conducted in accordance with the provisions of the Declaration of Helsinki, FDA regulations 21 CFR 50, 54, 56, and 312.50, and the ICH guidelines on GCP (ICH E6).

The clinical research coordinator will regularly inspect all CRFs, study documents, and research facilities associated with this study during and after completion of the study.

The study site may also be subject to inspection by the FDA, IRB, or other regulatory agencies. The Sponsor should be promptly notified of any audit scheduled with any regulatory agency.

A protocol deviation is any noncompliance with the clinical trial protocol or ICH GCP requirements. The noncompliance may be either on the part of the participant, the investigator, or the study site staff.

It is the responsibility of the site investigator to use continuous vigilance to identify and report deviations. The Investigator may not deviate from the protocol without a formal protocol amendment having been established and approved by the IRB, except when necessary to eliminate imminent hazards to the subject or when the change(s) involve only logistical or administrative aspects of the trial. Deviations should be reported promptly to the Sponsor and may also require reporting to the IRB.

In the event of serious or repeated deviations, corrective and preventative actions are to be developed by the site and implemented promptly. A deviation may result in the subject having to be withdrawn from the trial, potentially rendering that subject non-evaluable.

#### **14.0 Potential Benefits to Subjects**

There may be no benefit to the subject for participation in this study.

#### **15.0 Withdrawal of Subjects**

Subjects will be withdrawn from the study if they are unable to complete the tasks in the study protocol. In addition, if they experience an adverse event in which the investigator does not feel that the subjects should continue, they will be withdrawn.

The data from a subject that withdraws or is terminated from the study will not be included in the analysis.

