**[contact]**

**[[contact]](mailto:[contact])**

## **1.0 Objectives**

The goal of this prospective observational pilot study is to evaluate the tolerability and safety of RESTASIS (cyclosporine ophthalmic solution 0.05%) when added to the PROSE (Prosthetic Replacement of the Ocular Surface Ecosystem) lens reservoir in patients with ocular surface disease (OSD). Secondary endpoints include early (1-month) efficacy data for ocular signs and symptoms.

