#### **5.0 Number of Subjects**

This study will enroll a minimum of 10 subjects. We expect an approximate 10% drop-out rate, so we will expect to recruit approximately 12 subjects; and the first 10 to be eligible and complete the study will be used for data analysis. All subjects will receive the study drug, Restasis (cyclosporine ophthalmic solution 0.05%).

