**Visit 2: (1 Week post Restasis dispensing)**

- a. Update past medical history, past ocular history, allergies, medications
- b. Visual acuity assessments of both eyes (logMAR)
- c. Subject's evaluation of symptoms via OSDI
- d. Tolerability questionnaire
- e. Oculus Keratograph 5M R-Scan with lens (automatic classification of redness)
- f. Remove lens
- g. Oculus Keratograph 5M R-Scan without lens (automatic classification of redness)
- h. Slit lamp examination (without lens) including:
  - a. anterior segment and ocular surface
  - b. conjunctival redness (Efron Grading Scale, Modified Efron Grading Scale)
  - c. corneal staining with sodium fluorescein (NEI Grading System)
  - d. conjunctival staining with lissamine green (NEI Grading System)

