## 9.0 Study Endpoints

The study endpoints to analyze safety, tolerability and efficacy are as follows:

- a) Visual Acuity (logMAR)
- b) Tolerability questionnaire
- c) Ocular Surface Disease Index (OSDI)
- d) Corneal staining with sodium fluorescein (NEI Grading System)
- e) Conjunctival staining with lissamine green (NEI Grading System)
- f) Conjunctival redness, Efron and modified Efron scale
- g) Oculus Keratograph 5M R-Scan value

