## 10.0 Procedures Involved

The following table outlines each of the study visits and tells what procedures will be done at each visit:

Procedure	Length of Time Required for Participants
VISIT 1A: Initial Evaluation	
Informed consent & HIPAA	30 minutes
General History and medications	3 minutes
Visual Acuity	2 minutes
Tolerability Survey & OSDI	10 minutes
Slit-lamp Examination with assessment of PROSE devices	5 minutes
R-scan (pre and post PROSE removal)	10 minutes
Slit-lamp examination (after lens removal)	5 minutes
Instructions and dispensing product	10 minutes
TOTAL TIME	75 minutes

Procedure	Length of Time Required for Participants
VISIT 1B: Evaluation after 2 weeks with buffered saline	
General History and medications	3 minutes

Visual Acuity	2 minutes
Tolerability Survey & OSDI	10 minutes
Slit-lamp examination (after lens removal)	5 minutes
R-scan (pre and post PROSE removal)	10 minutes
Instructions and dispensing product	10 minutes
TOTAL TIME	40 minutes

Procedure	Length of Time Required for Participants
VISIT 2: Week 1 after dispense Restasis	
General History and medications	3 minutes
Visual Acuity	2 minutes
Tolerability Survey & OSDI	10 minutes
R-scan (pre and post PROSE removal)	10 minutes
Slit-lamp Examination (after lens removal)	10 minutes
TOTAL TIME	35 minutes

Procedure	Length of Time Required for Participants
VISIT 3: Week 4 after dispense Restasis	
General History and medications	3 minutes
Visual Acuity	2 minutes
Tolerability Survey & OSDI	10 minutes
R-scan (pre and post PROSE removal)	10 minutes
Slit-lamp Examination (after lens removal)	10 minutes
TOTAL TIME	35 minutes

Figure 1. Table including organization of examinations done at each study visit

Test	Description
General History and Medications	Participants will be asked questions about their general, ocular and medication use histories along with contact lens use history if applicable.
Lens Evaluation	The PROSE device fit and vision will be evaluated.
Visual Acuity	The participant's vision in each eye while wearing lenses will be measured with a high contrast visual acuity chart. The participant will be asked to cover one eye and read the chart, and this procedure will be repeated for the other eye.

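### Data from withdrawn subjects are excluded, so a tolerability study analyses only those who stayed to week 4

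*Protocol*

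**What the plan says.** Section 1.0 gives the goal of this single-arm pilot as to "evaluate the tolerability and safety of RESTASIS" placed in the PROSE lens reservoir. One-month efficacy is secondary.

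Section 15.0 withdraws subjects who cannot carry out the protocol tasks, and adds that "if they experience an adverse event in which the investigator does not feel that the subjects should continue, they will be withdrawn". Its closing sentence is "The data from a subject that withdraws or is terminated from the study will not be included in the analysis". It makes no exception for safety or tolerability data.

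Section 5.0 points the same way. About 12 subjects are to be recruited, allowing for roughly 10% drop-out, and "the first 10 to be eligible and complete the study will be used for data analysis".

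Section 9.0 opens its list of seven measures with "The study endpoints to analyze safety, tolerability and efficacy are as follows", so one set of measures serves all three purposes. After baseline these are taken at week 1 (Visit 2) and week 4 (Visit 3).

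Section 13.0 has every adverse event entered on a case report form whether or not it is related, with the action taken, and reported to the principal investigator and the IRB.

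The SAP compares post-treatment with baseline values by paired t-test and mentions two-way ANOVA. It defines no analysis set, no missing-data rule and no handling of subjects who stop.

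**The concern.** In a tolerability study, giving up the treatment because it is not tolerated is an outcome. It is not merely a reason for missing data. Sections 5.0 and 15.0 together treat it as missing data and then take the subject out of the analysis. Because recruitment exceeds the analysed number, a later completer fills the place and the final count of 10 shows no trace of the loss.

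The exclusion is also selective. Subjects most likely to leave because of an adverse event are those with the worst experience of the drop. Any summary of the questionnaire, OSDI, staining, redness or acuity limited to completers would then tend to look better than the experience of everyone dosed. At stake is whether the pilot's answer on tolerability describes all who tried the method or only those who stayed to week 4.

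**Working it through.** **Inputs.** From Section 5.0: 10 analysed, about 12 recruited, about 10% drop-out. From Section 15.0: withdrawn subjects' data excluded. The documents give no rate of stopping Restasis, so stopping counts of 1 and 2 and stopping rates of 2%, 5% and 10% are assumptions. The top rate equals the plan's drop-out for all causes.

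**1. The plan's own figure.** 10 / (1 − 0.10) = 11.1, rounded up to 12. The stated recruitment reproduces, and up to two of 12 can be lost with the analysed number still 10.

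**2. Stopping rate in the analysed set.** A subject who stops for intolerance is withdrawn, and a withdrawn subject is not analysed. The count is therefore 0 of 10 whatever happened. The exact (Clopper-Pearson) 95% upper limit is 1 − 0.025^(1/10) = 30.8%.

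**3. Stopping rate among everyone dosed.** Exact 95% intervals:

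| Stopped / dosed | Rate | 95% CI | Completer set shows |
|---|---|---|---|
| 1 / 11 | 9.1% | 0.2% to 41.3% | 0/10 |
| 1 / 12 | 8.3% | 0.2% to 38.5% | 0/10 |
| 2 / 12 | 16.7% | 2.1% to 48.4% | 0/10 |

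Twelve dosed is an upper case on the planned recruitment. Some of the 12 may prove ineligible, and Group B subjects may leave during the two weeks on Purilens before any Restasis.

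**4. Chance that the rule removes at least one such subject.** The formula is 1 − (1 − p)^n.

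| Assumed p | n = 12 | n = 10 |
|---|---|---|
| 2% | 1 − 0.98^12 = 22% | 1 − 0.98^10 = 18% |
| 5% | 1 − 0.95^12 = 46% | 1 − 0.95^10 = 40% |
| 10% | 1 − 0.90^12 = 72% | 1 − 0.90^10 = 65% |

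Intolerance is only one reason for dropping out, so on the plan's own 10% the last row is a ceiling.

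**5. Endpoint data.** A subject who stops before Visit 2 has no required post-baseline assessment. One who stops at or after "Visit 2: (1 Week post Restasis dispensing") has the full week 1 assessment on file. Collection thus falls short by two assessments or by one, but the analysis loses both in either case, because the exclusion covers all of a withdrawn subject's data.

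**The case against.** The strongest reply is that Section 13.0 already handles safety. Adverse events are examined when needed, treated, recorded with the action taken, and reported. On this view the exclusion in Section 15.0 concerns only the comparison with baseline, which a subject without a follow-up value could not enter anyway. The first part stands: the records exist and subjects are not left without care. The second does not close the gap. The exclusion sentence carries no such limit, it also drops a week 1 assessment that could be compared with baseline, and neither document calls for a summary of all dosed subjects.

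A second reply is that the stopping rate is not one of the seven endpoints and that the intervals above overlap heavily. Both are true. The contrast shows only that the completer set cannot display a stopper. It is not a test between two rates, and the bias in any one endpoint cannot be estimated from the documents.

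A third is that this is a small pilot, described in Section 10.0 as mainly observational. That favours a plain count of stoppers, which needs no power.

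A reader might also infer more than the documents support:

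- That the analysed subjects are only those who tolerated the drop. Completers may still report burning or redness at weeks 1 and 4, and those scores are analysed. The selection is on staying in the study.
- That the 17% ocular burning figure in Section 12.0 predicts stopping. It is an adverse reaction rate, and the documents do not link it to discontinuation.
- That the lack of an exit visit or off-drug follow-up is itself an error. Such procedures would be optional in a pilot of this size, and the SAP, dated 8/27/2024 and written in the past tense, suggests that collection is over.

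**Conclusion.** The concern holds as a fault in the analysis set. Followed as written, Sections 5.0 and 15.0 exclude subjects who stop Restasis for intolerance from a study whose main question is tolerability and safety, and the SAP does not bring them back. Stopping for intolerance is fixed at 0/10 (0% to 30.8%), where the figure among those dosed could be 1/12 (8.3%) or 2/12 (16.7%).

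This rests on two assumptions: that a subject who gives up the drop is withdrawn, as Section 15.0 indicates, and that up to 12 are dosed. The chance that it matters, 22% to 72% with 12 dosed and 18% to 65% with 10, depends on assumed stopping rates of 2% to 10%. The documents do not show that anyone stopped, so this is a weakness of the rule and no evidence that the reported result is wrong. It should be corrected because the correction is cheap and bears on the main objective.

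**What to change.** - **Protocol Section 15.0.** Replace the exclusion sentence with, for example: *Safety and tolerability will be reported for every subject who received at least one dose of Restasis, with the number who stopped, when and why, their adverse events, and any Visit 2 data they have.*
- **Protocol Section 5.0.** Limit the rule on the first 10 completers to the paired comparison with baseline.
- **SAP.** Name the two sets: all dosed subjects for safety and tolerability, and the 10 completers for the paired comparison.
- **If the analysis has already been run.** Add the all-dosed table and label it as added later.

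The cost is one extra table, built from the adverse event and action records that Section 13.0 already requires and from any week 1 data on file. No visit is added and the paired comparison is unchanged. The downside for the sponsor is that the tolerability result may look less favourable.

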#### **7.0 Multi-Site Research Communication – N/A**

#### **8.0 Study Timelines**

The total duration of the subjects' participation in the study will be between 4-6 weeks. It is anticipated that to enroll all study subjects, it will take approximately 8 months. The estimated date for completion of this study is 12 months after the start of recruitment.

The study will enroll 2 groups of subjects:

- Group A: Those subjects already using preservative free buffered normal saline (Purilens) at the time of enrollment to the study

- Group B: Those subjects NOT currently using preservative free buffered normal saline (Purilens) at the time of enrollment but who are willing to be switched to preservative free buffered normal saline (Purilens) as part of the study protocol

Visit 1A:

- a. Completion of informed consent
- b. Collect past medical history, past ocular history, allergies, medications as well as habitual contact lens information, including lens design, power, and diameter.
- c. Subject's evaluation of symptoms via a baseline tolerability questionnaire and baseline Ocular Surface Disease Index (OSDI)
- d. Visual acuity assessments of both eyes (logMAR)
- e. Baseline assessment of PROSE device:
  - a. Confirm acceptable fit
- f. Baseline Oculus Keratograph 5M R-Scan with lens (automatic classification of redness)
- g. Remove lens
- h. Baseline Oculus Keratograph 5M R-Scan without lens (automatic classification of redness)
- i. Baseline slit lamp examination (without lens) including:
  - a. anterior segment and ocular surface
  - b. conjunctival redness (Efron Grading Scale, Modified Efron Grading Scale)
  - c. corneal staining with sodium fluorescein (NEI Grading System)
  - d. conjunctival staining with lissamine green (NEI Grading System)
- j. Initiation of study, with either:
  - a. Group A (subjects currently using Purilens): Dispense Restasis for initiation of usage in device bowl
    - i. Instructions for use: 1 drop of RESTASIS in the lens bowl followed by filling the remainder of the lens bowl with Purilens qAM. After 6 consecutive hours of wear, remove and reapply lens with 1 drop of RESTASIS in the lens bowl followed by filling the remainder of the lens bowl with Purilens. Wear lens without removal for at least 4 more consecutive hours.
  - b. Group B (subjects NOT currently using Purilens): the subject will be provided Purilens for use over the next two weeks and return for Visit 1B
- k. Reapply lens and wait 15 minutes

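### In a study of tolerability and safety, subjects who withdraw, including for an adverse event, are dropped from the analysis, so the planned results describe completers only

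*Protocol*

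**What the plan says.** Protocol section 1.0 gives the goal as to "evaluate the tolerability and safety of RESTASIS" in the PROSE reservoir, with one-month efficacy as secondary. The Statistical Analysis text in section 10.0 likewise presents the results as an early answer on tolerability.

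Section 15.0 gives two routes out of the study. The first is: "Subjects will be withdrawn from the study if they are unable to complete the tasks in the study protocol". The second concerns safety: "if they experience an adverse event in which the investigator does not feel that the subjects should continue, they will be withdrawn". It then sets the analysis rule: "The data from a subject that withdraws or is terminated from the study will not be included in the analysis". No exception is made for safety or tolerability data.

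Section 5.0 reaches the same result by another path. It says "We expect an approximate 10% drop-out rate, so we will expect to recruit approximately 12 subjects", and that "the first 10 to be eligible and complete the study will be used for data analysis".

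Section 9.0 opens its endpoint list with "The study endpoints to analyze safety, tolerability and efficacy are as follows". The list has visual acuity, the tolerability questionnaire, OSDI, staining and redness. Neither adverse events nor withdrawals appear in it. The SAP compares post-treatment data with baseline by paired t-test and adds a two-way ANOVA. It defines no safety set, no withdrawal summary and no handling of leavers.

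**The concern.** In a tolerability study, stopping because of the treatment is itself an outcome, and often the most informative one. Here it is treated as a reason to delete the subject. Someone who answers the tolerability questionnaire at Week 1 and then stops for an adverse event loses even that recorded answer from the analysis.

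The first withdrawal route may act the same way. The protocol does not define the tasks a subject must be able to complete. If they include the wear schedule in section 8.0, which after the second instillation says "Wear lens without removal for at least 4 more consecutive hours", then a subject who cannot tolerate that wear with the drug in the bowl is withdrawn and excluded.

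At stake is the main conclusion. A report that the regimen was well tolerated in 10 subjects would mean only that 10 people who finished had finished. Changes in OSDI, staining and redness would also look too favourable if leavers did worse than completers. If subjects leave for unrelated reasons, those changes need not be biased.

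**Working it through.** **Inputs from the documents.** 10 completers to be analysed, about 10% drop-out from any cause, about 12 recruited (section 5.0); ocular burning in 17% in the drug's clinical trials (sections 12.0 and 13.0). **Assumptions.** The number dosed, independence of departures, and the share of drop-out due to an adverse event or intolerance. The documents give none of these.

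**1. The plan's own figure.** 10 / (1 − 0.10) = 11.1, rounded up to 12. This matches the stated recruitment. Expected drop-outs are 12 × 0.10 = 1.2.

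**2. How often the rule removes someone.** P(at least one leaver) = 1 − (1 − p)^n, where p is 10% times the assumed intolerance share:

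| Share of the 10% | p | n = 10 | n = 11 | n = 12 |
|---|---|---|---|---|
| All causes | 0.10 | 65% | 69% | 72% |
| Half | 0.05 | 40% | 43% | 46% |
| A quarter | 0.025 | 22% | 24% | 26% |

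For example, 1 − 0.90^12 = 0.718 and 1 − 0.975^11 = 0.243. The n = 10 column allows for recruits who are ineligible or who leave during Group B's two-week saline run-in, before any drug.

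**3. What the all-dosed summary would show** (exact Clopper-Pearson 95% intervals):

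- 1 intolerance leaver of 11 dosed: 9.1% (0.2% to 41.3%).
- 2 of 12 dosed: 16.7% (2.1% to 48.4%).

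Among completers the corresponding proportion is zero by construction, so an interval around it would carry no information.

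**4. Effect on mean changes.** Let C be the completers' mean change, L the leavers' mean change, k the leavers and n the dosed. The all-dosed mean is [(n − k)C + kL] / n, so the completers' mean differs from it by (k/n)(C − L). For 1 of 11 that is 1/11 = 9.1% of the gap; for 2 of 12 it is 2/12 = 16.7%. If there is no gap, there is no shift.

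**5. Effect on an adverse-event rate.** Suppose burning truly occurs in 17%, a share q of those affected withdraw, and nobody else does. The rate among completers is 0.17(1 − q) / (1 − 0.17q). With q = 0.25 this is 0.1275 / 0.9575 = 13.3%; with q = 0.5 it is 0.085 / 0.915 = 9.3%; with q = 1 it is 0%. The 17% is an occurrence rate from the drug's own trials, not a withdrawal rate or a rate for reservoir use, so this shows direction only.

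**6. Does anything bring leavers back?** Section 13.0 requires every adverse event to be recorded on a case report form and lists discontinuation as an action to document. That is recording and reporting. The analysis text in sections 10.0 and 23.0 describes comparisons with baseline and general modelling techniques, with no commitment to summarise events or withdrawals. The SAP's remark that every patient received treatment justifies the paired test; it does not define an all-dosed analysis set.

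**The case against.** The best defence has five parts.

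- **Adverse events are not lost.** They are recorded, reported to the principal investigator and the IRB, and section 15.0 does not forbid listing them. A study described as mainly observational leaves room for descriptive reporting. This is true, and it limits the concern to the analysis. But no summary is committed to, and the exclusion sentence has no exception.
- **The wear-schedule route is speculative.** Inclusion criteria 11 to 13 and exclusion criterion 15 already screen for ability to wear the device for 6 hours and then at least 4 more. This makes that route secondary. It does not close it, because screening precedes use of the drug in the bowl, and the adverse-event route is sufficient alone.
- **Section 13.0 is softer.** It says a deviation may lead to withdrawal and potentially to a subject being non-evaluable. That wording is conditional and does not override the flat rule in section 15.0.
- **The size is uncertain.** If only a tenth of drop-out were intolerance, the chance of at least one such leaver would be about 10% to 11%. On the quarter-share assumption with 11 or 12 dosed, there is a 74% to 76% chance that no such leaver is removed. The documents do not say whether anyone withdrew. This stands: the probabilities illustrate and do not show that bias occurred.
- **It is a small pilot.** Small size makes each excluded subject weigh more, and a descriptive result still needs the right denominator.

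**Conclusion.** The concern holds and should be fixed before the results are relied on. Sections 5.0 and 15.0 take treatment-related leavers out of the analysis that is supposed to measure tolerability, and nothing elsewhere in the protocol or SAP restores them. The fault is in the written rule and does not depend on how many subjects left.

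Its practical size does depend on that number and on why they left, and neither is given. With 11 or 12 dosed and independent departures at 10%, someone is more likely than not to be excluded. The chance that at least one is an intolerance case follows the assumed share. A single such case would be about 9% of those dosed. The before/after changes are distorted only to the extent that leavers fared differently.

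**What to change.** Replace the exclusion sentence in section 15.0 and the first-10-completers rule in section 5.0, and add a paragraph to the SAP:

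1. Summarise safety and tolerability in every subject who received at least one dose of study drug. List subjects lost before dosing separately.
2. Report all adverse events and all withdrawals in dosed subjects with reasons, including the number and proportion who stopped for an adverse event or intolerance, with an exact interval.
3. Base the Week 1 change on every dosed subject with a Week 1 value, and the Week 4 change on every dosed subject with a Week 4 value, including completers after the tenth. Beside the Week 4 result, state how many dosed subjects are missing and why, and describe the result as applying to those who remained.
4. Keep the first-10-completers analysis as a sensitivity analysis.

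The first two items repair the main defect. The third stops recorded Week 1 data from being discarded and removes an arbitrary cut at ten. The SAP is written in the past tense, so if the analysis has been done, rerun it on these sets and disclose that they were changed afterwards.

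The cost is two protocol sentences, one SAP paragraph and probably a small reanalysis of data already recorded. No new subjects, visits or measurements are needed, and no clinical rule changes. The tolerability result may look less favourable, and the Week 4 comparison still cannot speak for those who left.
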